# 6.3.3 Management of Nausea and Vomiting

For subjects who experience nausea and/or vomiting in association with APR-246, treatment with anti-emetics is recommended per institutional guidelines. Use of medications that prolong the cardiac QT interval is discouraged. For subjects who receive medications known to cause QT prolongation, the QT must be monitored via ECG before and after the APR-246 infusion.

• If QTc > 501 msec is observed in a subject concomitantly treated with another QT interval prolonging drug, this drug should be stopped and treatment with APR-246 may be restarted when QTc < 470 msec (refer to Section6.3.1).

A list of suggested rescue medications is provided below in Table 3.
--

Drug	Dosage	QT Prolongation a
Ondansetron	8 mg orally (PO) administered 30 minutes before	Yes
	the start of infusion or per label	
Dolasetron	100 mg PO administered within one	Yes
	hour before start of infusion or per label	
Palonosetron	0.5 mg PO administered approximately one	No
	hour prior to the start of infusion or per label	
Prochlorperazine	10 mg PO three times daily. Continue until the	No
	end of Day 4 of the cycle. When used	
	prophylactically in subsequent cycles, start the	
	day prior to Day 1 administration of APR-246	

Table 3. Medications for Managements of Nausea and Vomiting	

a Please refer to Section 6.3.1 for details on concurrent administration of medications known to cause QTc interval prolongation.

#### 6.3.4 Management of Infusion Reactions

#### 6.3.4.1 APR-246

If a subject experiences an infusion reaction considered related to APR-246, the infusion should be immediately interrupted and appropriate medical care (e.g., epinephrine, oxygen, H1 and H2 antagonists, and/or corticosteroids) administered.

#### 6.3.4.2 Pembrolizumab

Pembrolizumab is to be administered only under the care of a physician experienced in the use of pembrolizumab in treating subjects with solid tumor malignancies.

Dose Modification and Toxicity Management for Immune-related AEs Associated with Pembrolizumab

AEs associated with pembrolizumab exposure may represent an immunologic etiology. These immune-related AEs may occur shortly after the first dose or several months after the last dose of pembrolizumab treatment and may affect more than one body system simultaneously. Therefore, early recognition and initiation of treatment is critical to reduce complications. In clinical studies, most AEs were reversible and could be managed with interruptions of pembrolizumab, administration of corticosteroids and/or other supportive care. For suspected AEs, ensure adequate evaluation to confirm etiology or exclude other causes. Additional procedures or tests such as bronchoscopy, endoscopy, skin biopsy may be included as part of the evaluation. Based on the severity of AEs, withhold or permanently discontinue pembrolizumab and administer corticosteroids. Dose modification and toxicity management guidelines for ARs associated with pembrolizumab are provided in the USPI.

# Dose Modification and Toxicity Management of Infusion Reactions Related to Pembrolizumab

Pembrolizumab may cause severe or life-threatening infusion-reactions including severe hypersensitivity or anaphylaxis. Signs and symptoms usually develop during or shortly after drug infusion and generally resolve completely within 24 hours of completion of infusion. Dose modification and toxicity management guidelines on pembrolizumab associated infusion reaction are provided in the USPI.

# 6.4 Concomitant Treatment

Subjects must not receive any other concurrent anti-cancer therapy, including investigational anti-cancer agents, while on study treatment.

Subjects may continue their baseline medication(s) as long as they are not prohibited. Prohibited mediations include systemic immunosuppressive treatment [ex. prednisone  $\geq$  10 mg/day (or equivalent corticosteroid)], live vaccines and investigational anti-tumor products. Palliative and supportive care (e.g., anti-emetics, bisphosphonates) for disease-related symptoms may be utilized according to institutional practices. AEs will be treated as clinically indicated. All concomitant medications should be recorded in the eCRF.

If the subject develops an acute infusion reaction ( $\geq$  Grade 2), the infusion must be interrupted until the reaction is resolved to  $\leq$  Grade 1. Premedication (e.g., systemic corticosteroids) may be used as required.

# 6.5 Monitoring Subject Compliance

This study will be monitored by Aprea Therapeutics, Inc. or its Contract Research Organization (CRO) according to ICH E6 guidelines of GCP. The study site monitor will regularly visit the study sites to ensure that the study is conducted according to the protocol and GCP principles. All instances of protocol deviations will be entered and reviewed by the investigator, Sponsor and appropriate designee.

# 7.0 STUDY EVALUATIONS

# 7.1 Schedule of Study Evaluations

Study evaluations are summarized in Table 4 and described in Sections 7.2 through 7.4.

#### Phase 1/2 Study of APR-246 in Combination with Pembrolizumab in Subjects with Solid Tumor Malignancies

# Table 4. Study Calendar

Study Calendar	Screening a						Cycle 2 and Subsequent Cycles				End of	Long-	
Evaluation a	(28 days)	D1	D2	D3	D4	D8 b, e	D15 b, e	D1 c	D2	D3	D4		Term Follow- up s
Informed consent	×												
Medical history d	×												
Physical examination e	×	×						×				×	
Height	×												
Weight	×	×						×				×	
Vital signs e	×	×	×	×	×			×	×	×	×	×	
ECOG PS	×	×						×				×	
APR-246 f		×	×	×	×			×	×	×	×		
Pembrolizumab g				×						×			
Disease assessment h	×							× h				×	
Hematology i	×	×				×	×	×				×	
Serum chemistry j	×	×				×	×	×				×	
Pregnancy test k	×												
ECG 	×	×I	×I	×I	×I			×					
APR-246 PK sample m		×	×	×	×			×	×	×	×		
Archival tissue collection n	×												
Fresh tissue biopsy °	×							×					
Blood for biomarkers p	×	×						×				×	
Blood for PBMC q	×	×						×				×	
Clinical toxicity assessment		Starting at the time of study treatment initiation through 30 days after last dose t											
Concomitant medications		Reviewed throughout study											
Survival												×	×

#### Footnotes to Study Calendar

- a. All screening/baseline evaluations are performed within 28 days prior to the start of study treatment. In the event that a visit or test cannot be scheduled on the exact visit day, a window of ±3 days is allowable.
- b. A window of ±3 days applies to this study visit.
- c. After the first cycle, Day 1 evaluations of subsequent cycles are to be done within 3 days prior to next cycle drug administration.
- d. Full medical history is obtained at screening for safety and eligibility purposes; this will include any clinically significant findings from 28 days prior to screening date.
- e. Physical exam and vital signs (including blood pressure, heart rate, respiration rate and temperature) are completed for safety purposes and clinically significant items are recorded as AEs where appropriate. Vital signs are collected prior to APR-246 infusion, 2 hours into infusion and at EOI (±30 minutes at all time points).
- f. APR-246 is administered IV on Days 1–4 of each 21-day cycle.
- g. Pembrolizumab at a dose of 200 mg is to be administered on Day 3 ±1 day of each cycle before the Day 3 dose of APR-246.
- h. Disease assessment should be conducted every 9 weeks (±3 days) after initiating study treatment, prior to initiation of each odd treatment cycle starting at Week 9, then every 6 weeks through the first year and then every 9 weeks, thereafter. Magnetic resonance imaging (MRI) may be used instead of computed tomography (CT) for head, neck, abdomen, and pelvis; however, the chest must be assessed using CT. Chest disease may not be followed using chest x-ray. Positron-emission tomography (PET) scanning should not be used, but PET/CT may be used if CT component is with contrast enhancement and of diagnostic quality. The same modality (CT, MRI, and/or PET) that is used for baseline disease assessment should be used throughout the study.
- i. Hematology must include complete blood count with differential.
- j. Serum chemistry must include sodium, potassium, chloride, CO2, blood urea nitrogen (BUN), creatinine, glucose, calcium, albumin, total protein, total bilirubin, AST, ALT, alkaline phosphatase, Thyroid Stimulating Hormone (TSH) and free T4.
- k. Serum or urine βhCG must be performed within 7 days prior to study treatment initiation in female subjects of childbearing potential.
- I. Standard 12-lead ECGs in triplicate at screening, on Days 1–4 of Cycle 1 and on Days 1 of each subsequent cycle with subject in a semi-recumbent position. Please consult Table 6 for ECG collection schedule.
- m. Please consult Section 8.5 for PK collection schedule.
- n. Tumor block or 20 unstained, 4-µm thick, paraffine-embedded tumor slides from an archival tissue sample, if available.

- Optional: Percutaneous or endoscopic biopsy of a tumor lesion will be only performed at baseline (within 2 weeks prior to treatment initiation) and at Cycle 2 Day 1 (±5 days). Biopsy samples will be formalin-fixed, paraffin embedded and snap frozen.
- p. Blood for serum analysis is collected on specific 5-mL dry tubes at screening, prior to treatment initiation at Cycle 1 Day 1, and at the time of second tumor biopsy/or prior to Cycle 2 Day 1 treatment if no biopsy is done.
- q. Blood for PBMC isolation is collected in four 10-mL CPT tubes (total, 40 mL) at screening, prior to treatment initiation at Cycle 1 Day 1, and at the time of second tumor biopsy/or prior to Cycle 2 Day 1 treatment, if no biopsy is done. Additional PBMCs will be collected prior to Cycle 5 Day 1 treatment and 30 days after treatment discontinuation.
- r. Subjects discontinuing treatment should complete their end of treatment visit 30 days after their last dose of APR-246. Physical exam, vital signs, clinical toxicity assessment, hematology, serum chemistry and disease assessment should be performed, if feasible.
- s. Long-term follow up can be done remotely (e.g. via telephone, via local practitioner or via review of medical records). Assuming there is no withdrawal of consent, subjects who stop study treatment for any reason (e.g. toxicity, PD) will continue long-term follow-up (see Section 7.4). If a subject is removed from the study due to unacceptable AEs, the event(s) will be followed until resolution or stabilization of the AE.
- t. AE description, grade and start date and resolution date should be documented.

# 7.1.1 Screening

All screening evaluations are to be performed within approximately 28 days of study treatment initiation, unless otherwise noted.

- Signed written informed consent
- Medical history
- Physical examination
- Height
- Weight
- ECOG performance status (APPENDIX II)
- Vital signs, including blood pressure, heart rate, respiration rate and temperature
- Hematology, including complete blood count with white blood cell differential.
- Serum chemistry, including sodium, potassium, chloride, CO2, BUN, creatinine, glucose, calcium, albumin, total protein, total bilirubin, AST, ALT, alkaline phosphatase, TSH and free T4
- Creatinine clearance (Cockcroft-Gault method; APPENDIX I)
- Serum or urine βhCG must be performed within 7 days prior to study treatment initiation for female subjects of childbearing potential.
- ECG: standard 12-lead ECGs with subject in a semi-recumbent position in triplicate.
- Concomitant medication review
- Optional: Archival tissue collection
- Optional: Fresh tissue biopsy
- Blood for biomarkers
- Blood for PBMC
- Baseline disease assessment at a minimum must include imaging of chest, abdomen and pelvis (CT, MRI, and/or PET) for subjects with gastric/GEJ adenocarcinoma, urothelial cancer and non-small cell lung cancer. The same modality should be used throughout the study.

# 7.2 Pre-Study Assessments

Prior to performing any procedures or assessments, the nature of the study and the potential risks associated with the trial will be explained to all subject candidates and written informed consent will be obtained. Subjects who choose to participate will have to consent to the biobanking program and will be asked to sign the mandatory section in the main study consent form related to biobank samples. Evaluations obtained as part of routine medical care and performed during the screening period may be used in place of the study specific evaluations. Subjects will acknowledge and agree to the possible use of this information for the study by giving informed consent.

# 7.2.1 Cycle 1

# 7.2.1.1 Cycle 1 Days 1–4

Day 1 examinations marked \* do not need to be repeated if already performed within 3 days prior to Day 1 Cycle 1.

- Clinical toxicity assessment
- Concomitant medications review
- Physical examination: Day 1\*
- Weight: Day 1\*
- ECOG performance status (Day 1\*; APPENDIX II)
- Vital signs, including blood pressure, heart rate, respiration rate and temperature, collected 2 hours into APR-246 infusion (± 30 min) and at EOI (± 30 min)
- Hematology (Day 1\*), including complete blood count with white blood cell differential
- Serum chemistry (Day 1\*), including sodium, potassium, chloride, CO2, BUN, creatinine, glucose, calcium, albumin, total protein, total bilirubin, AST, ALT, alkaline phosphatase, TSH and free T4
- Blood for biomarkers (Day 1\*)
- Blood for PBMC (Day 1\*)
- ECG: standard 12-lead ECG with subject in a semi-recumbent position; pre-dose (prior to the APR-246 PK blood draw before the infusion) and at the EOI, per Table 6
- APR-246 administration: Days 1–4
- Blood sample for APR-246 pharmacokinetics: on Days 1, 2, 3 and 4, per Table 5
- Pembrolizumab at a dose of 200 mg is to be administered on Day 3 ±1 day of each cycle before the Day 3 dose of APR-246

# 7.2.1.2 Cycle 1 Days 8 and 15 (±3 Days)

- Clinical toxicity assessment
- Concomitant medications review
- Hematology, including complete blood count with white blood cell differential
- Serum chemistry, including sodium, potassium, chloride, CO2, BUN, creatinine, glucose, calcium, albumin, total protein, total bilirubin, AST, ALT, alkaline phosphatase, TSH and free T4

# 7.2.2 Cycle 2 and Onwards (Cycle 3+) Day 1 (±3 Days)

These tests should be performed prior to first dose

- Clinical toxicity assessment
- Concomitant medications review
- Physical examination: Day 1\*

Aprea Therapeutics, Inc. Protocol Number A20-11195

- Weight
- ECOG performance status (Day 1; APPENDIX II)
- Vital signs
- APR-246 administration: Days 1–4
- Hematology (Day 1\*), including complete blood count with white blood cell differential
- Serum chemistry (Day 1\*), including sodium, potassium, chloride, CO2, BUN, creatinine, glucose, calcium, albumin, total protein, total bilirubin, AST, ALT, alkaline phosphatase, TSH and free T4
- Blood for biomarkers (Cycle 2)
- Blood for PBMC (Cycle 2 and Cycle 5)
- Fresh tissue biopsy
- ECG: standard 12-lead ECGs with subject in semi-recumbent position before APR-246 infusion on Day 1 see Table 6
- Cycle 3 and onwards, prior to each odd cycle: disease assessment

# 7.2.2.1 Cycle 2 and Onwards Days 2–4

- Clinical toxicity assessment
- Concomitant medications review
- Vital signs, including blood pressure, heart rate, respiration rate and temperature, collected 2 hours into APR-246 infusion (± 30 min) and at EOI (± 30 min)
- Pembrolizumab at a dose of 200 mg is to be administered on Day 3 ±1 day of each cycle before the Day 3 dose of APR-246
- APR-246 administration: Days 1–4
- *Only Cycle 3*: Blood sample for APR-246 pharmacokinetics: on Days 1, 2, 3 and 4, per Table 5

# 7.3 End of Treatment Visit

This visit should take place 30 days after the last dose of study treatment, if treatment is stopped early for any reasons.

- Physical examination
- Weight
- Vital signs
- Disease assessment
- ECOG performance status (APPENDIX II)
- Hematology, including complete blood count with white blood cell differential
- Serum chemistry, including sodium, potassium, chloride, CO2, BUN, creatinine, glucose, calcium, albumin, total protein, total bilirubin, AST, ALT, alkaline phosphatase, TSH and free T4
- Blood for biomarkers

Aprea Therapeutics, Inc. Protocol Number A20-11195

- Blood for PBMC
- Clinical toxicity assessment up to 30 days after the last dose
- Survival follow-up

# 7.4 Long-Term Follow-Up

Long-term follow-up can be done remotely (e.g. via telephone, via local practitioner or via review of medical records). After a subject is removed or withdrawn from the study, the subject will be followed for 1 year or until death, whichever occurs first. Off-treatment data on OS will be updated every 6 months or until death, whichever occurs first. If a subject is removed from the study due to unacceptable AEs, the event(s) will be followed until resolution or stabilization of the AE(s). Subjects who respond and discontinue study treatment for reasons other than PD should have response assessments and survival should be collected every 2 months until disease progression or death, whichever occurs first. After disease progression, data for survival should be collected every 6 months until death.

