	
 
advanced bladder/urothelial tumors that have progressed after first line treatment, or who are intolerant to first line treatment, or who are unable to receive first line treatment with cisplatin-based chemotherapy. Patients with clinically stable, known metastatic tumors to the CNS are eligible with Medical Monitor approval. CNS radiography is not required in the absence of suspicion for clinical involvement. Prior treatment with anti-PD-1/anti-PD-L1 therapy is prohibited is prohibited.
 
Patients with histologically and/or cytologically confirmed diagnosis of advanced NSCLC previously treated with anti-PD-1 or anti-PD-L1 therapy. Patients with clinically stable, known metastatic tumors to the CNS are eligible with Medical Monitor approval. CNS radiography is not required in the absence of advanced NSCLC previously treated with anti-PD-1 or anti-PD-L1 therapy. Patients with clinically stable, known metastatic tumors to the CNS are eligible with Medical Monitor approval. CNS radiography is not required in the absence of suspicion for clinical involvement.
 

Duration of Follow-Up	Subjects will be followed as per the Study Calendar. After a subject is removed or withdrawn from study treatment, the subject will be followed for up to 1 year or until death, whichever occurs first.
	Off-treatment data on OS will be updated every 6 months or until death, whichever occurs first. If a subject is removed from the study due to unacceptable AEs, the event(s) will be followed until resolution or stabilization of the AE(s). Subjects who respond and discontinue study treatment for reasons other than progressive disease (PD) should have response assessments and survival should be collected every 2 months until disease progression or death, whichever occurs first. After disease progression, data for survival should be collected every 6 months until death.
	Criteria for Removal from Study Treatment
	Study treatment can continue for subjects receiving clinical benefit, unless one or more withdrawal criteria are met, or at the subject's discretion, or if the study is terminated.
	1. Study Treatment Discontinuation
	Study treatment must be discontinued if:
	• There is evidence of disease progression. Subjects who have PD but who are continuing to derive clinical benefit in the opinion of the investigator may continue to receive study treatment.

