Generally, all the continuous variables will be summarized using n (number of subjects with available data), mean, standard deviation (StDev), median, and range (minimum and maximum). Categorical data will be summarized by frequency and percentage. Time to event data will be analyzed using Kaplan-Meier method, and the number and percentage of events, or censored, the first quartile at 25%, median with 95% confidence, and third quartile at 75% of survival time will be presented. The survival rate at the 3, 6, 9, and 12 months, and then 2, 3 and 5 years will be presented. All the study data will be listed.
Safety data including AEs, vital signs, laboratory data, electrocardiogram (ECG), physical exam, and ECOG performance status will be summarized in the safety population. AEs will be coded using the Medical Dictionary for Regulatory Activities (MedDRA) and graded using NCI-CTCAE v5.0 severity grade.
The efficacy endpoints in the safety lead-in portion will be listed only. In the expansion phase, all the rates (ORR, DCR, durable SD, CBR) will be summarized with 95% exact confidence intervals (Clopper and Pearson) by cohorts. The time to event

data (DOR, PFS, and OS) will be analyzed using Kaplan-Meier method and	the 1
corresponding survival plots will be produced.	

PK/safety relationships will be explored graphically and investigated by model-based analysis if appropriate.

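### The synopsis and Section 7.4 each set a 1-year follow-up limit beside survival collection until death, with different clock starts, and the only survival censoring rule sits under ORR instead of OS

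*Combined protocol and SAP*

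**What the plan says.** **The limit.** Section 7.4: "After a subject is removed or withdrawn from the study, the subject will be followed for 1 year or until death, whichever occurs first". The synopsis, under Duration of Follow-Up: "After a subject is removed or withdrawn from study treatment, the subject will be followed for up to 1 year or until death". The first year runs from leaving the study, the second from leaving treatment.

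**Open-ended survival collection, in the same paragraphs.** Both places state "Off-treatment data on OS will be updated every 6 months or until death, whichever occurs first", and both end with "After disease progression, data for survival should be collected every 6 months until death". Between these stands a rule for one subgroup: "Subjects who respond and discontinue study treatment for reasons other than PD should have response assessments and survival should be collected every 2 months", continuing to progression or death.

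**Who enters long-term follow-up.** Footnote s to Table 4: "subjects who stop study treatment for any reason (e.g. toxicity, PD) will continue long-term follow-up (see Section 7.4". Section 5.4.2 limits discontinuation from the study to death, loss to follow-up and withdrawn consent. Section 8.2 keeps imaging subjects who stop treatment without progression until they progress or start another anticancer therapy, with no 1-year limit.

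**Planned analysis.** The synopsis and Section 9.3 apply Kaplan-Meier to time-to-event data, and "The survival rate at the 3, 6, 9, and 12 months, and then 2, 3 and 5 years will be presented".

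**Censoring.** Section 8.4 and the synopsis define OS as treatment start to death and give no censoring rule. Section 8.2.1 and the synopsis say that ORR is measured until death and that survivors at data cutoff are censored when last known alive. The cutoff is not defined; Section 4.2 defines only the end of the study. The synopsis defers analysis detail to a SAP, and no separate SAP text is among the documents supplied.

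**The concern.** A site cannot tell from either paragraph whether survival contacts stop one year after treatment or go on until death. Sites that read it differently will collect different data, and no SAP can recover contacts that were never made.

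If the limit is applied from the end of treatment, a capped subject can be seen at 24, 36 or 60 months only after more than 12, 24 or 48 months on treatment. Late Kaplan-Meier estimates would then rest on a few long-treated subjects, and follow-up would depend on treatment duration and response, so the censoring could be informative.

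The misplaced sentence is a second defect. A response proportion has no censoring, so the text does nothing where it stands, and the endpoint that needs it lacks it.

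**Working it through.** The plan states no OS event count or power, so there is no figure to reproduce. The check has two parts: who is capped, and what that does to late OS.

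**1. Who is capped, by reading**
- *Literal 7.4 clock.* Under Section 5.4.2 a subject leaves the study only by death, loss to follow-up or withdrawn consent. A year counted from then caps almost nobody who is off treatment but still on study. However, 7.4 also writes "If a subject is removed from the study due to unacceptable AEs", and footnote s sends subjects who stop treatment to 7.4, so the end of treatment may be what is meant.
- *OS sentences govern.* Nobody is capped.
- *Post-progression sentence covers all progressors.* It names no subgroup. Progression is a ground for stopping treatment (Section 5.4.1), and Section 8.2 images the others until progression or new therapy. The clearest capped group is subjects who stop without progression and start new therapy first.
- *Synopsis limit applied to nearly everyone off treatment.* Only responders who stop without progression might be exempt.

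**2. Size**

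Inputs from the documents: landmarks at 24, 36 and 60 months; a limit of 12 months; at least 20 evaluable subjects per cohort (Section 9.1). Everything else is assumed. Treatment time T is exponential with median 4 months and no deaths on treatment. Later survival is exponential with median 8 months (scenario 1), or a 70/30 mixture of exponentials with medians 4 and 36 months (scenario 2). There is no study closure, so uncapped counts are upper limits.

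True OS:
- Scenario 1: S(t) = 2·2^(−t/8) − 2^(−t/4), giving S(12) = 58.2% and S(36) = 8.6%.
- Scenario 2: S(t) = 0.7(1 + t·ln2/4)·2^(−t/4) + 0.3[36·2^(−t/36) − 4·2^(−t/4)]/32, giving S(12) = 53.3% and S(36) = 17.9%.

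A capped subject is at risk at L only if T > L − 12 and the subject is alive at L. Because T is memoryless, that probability is 2^(−(L−12)/4)·S(12). With a share e followed to death and the same prognosis throughout,

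at risk of 20 = 20[e·S(L) + (1 − e)·2^(−(L−12)/4)·S(12)].

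At 36 months, 2^(−6) = 0.0156:
- e = 0, scenario 1: 20 × 0.0156 × 0.582 = 0.18.
- e = 0.7, scenario 2: 0.7 × 3.57 + 0.3 × 0.17 = 2.55.

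The OS columns are the large-sample Kaplan-Meier value from 2,000,000 simulated subjects (first row: true OS).

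| Followed to death | At risk of 20 at 36 mo, scen. 1 | OS 36/60 mo, scen. 1 | At risk of 20 at 36 mo, scen. 2 | OS 36/60 mo, scen. 2 |
|---|---|---|---|---|
| 100% | 1.73 | 8.6 / 1.1% | 3.57 | 17.9 / 10.7% |
| 90% | 1.57 | 8.7 / 1.1% | 3.23 | 17.7 / 10.5% |
| 70% | 1.26 | 8.9 / 1.2% | 2.55 | 17.2 / 10.2% |
| 0% | 0.18 | 11.4 / 2.2% | 0.17 | 10.6 / 2.2% |

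With everyone capped, the chance that nobody of 20 is at risk at 36 months, (1 − p)^20, is 83% and 85%, against 16% and 2% uncapped. The 36-month bias is +2.8 points in scenario 1 and −7.3 in scenario 2, so its direction is not known in advance. At 24 months the estimates are 25.7% against 23.4% and 23.7% against 26.8%. Those differences are well inside the standard error for 20 fully followed subjects: √(0.234 × 0.766/20) = 9.5 points and √(0.268 × 0.732/20) = 9.9 points. At 12 months nothing changes, because the cap cannot fall before 12 months.

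**3. Sensitivity to treatment time.** With everyone capped, the ceiling on subjects at risk at 36 months, before deaths, is 20·2^(−24/m): 0.3 for a median m of 4 months, 1.2 for 6 (1.25 before rounding), 5.0 for 12. With a 12-month median and later-survival medians of 6 to 12 months, 55-80% of those alive at 36 months would still be observed.

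**The case against.** The strongest reply is that the OS-specific text points one way. The six-monthly updates have no stated end other than death, the post-progression sentence covers progressors without restriction, Section 8.2 carries the rest towards progression, and the literal 7.4 clock caps almost no one. No sentence says that survival collection stops at one year. On this view the limit concerns general follow-up, and only the wording needs tidying.

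Much of this stands. A reader might infer from the limit that 3- and 5-year OS will be mostly unobservable. The documents do not support that as a general statement: it needs the synopsis clock, applied to nearly everyone off treatment, together with short treatment times. Five-year data could also be sparse with no limit at all (scenario 1: 0.2 of 20 at risk).

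What does not stand is that the text settles the matter. Neither paragraph ranks its sentences, and the synopsis sets its limit from the end of treatment.

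On censoring, a SAP may well supply the OS rule, and PFS and DOR have no stated censoring rule here either. So one cannot say that the rule is missing from the whole plan. The misplaced ORR text is wrong as written all the same.

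**Conclusion.** The conflict is real and needs no assumption to see: two paragraphs each contain a 1-year limit and open-ended survival collection, and they start the year at different events. Its effect on late OS runs from none, through under 1 point at 36 months (70-90% followed to death, same prognosis), to near-complete loss of subjects at risk at 36 and 60 months if the limit is applied to almost everyone and the treatment median is about 4 months. All time distributions and shares are assumptions; the documents give none. A capped group with a different prognosis would change the bias.

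OS is secondary and descriptive, so this is a minor-to-moderate point. The ORR/OS censoring misplacement is certain as a matter of text. The absence of an OS rule is established only for the documents supplied.

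**What to change.** 1. In Section 7.4 and the synopsis, state one survival rule for every subject who has not withdrawn consent: survival status every 6 months (more often where already stated), remotely if needed, until death, loss to follow-up or a common data cutoff. Say that the 1-year limit does not apply to survival status.
2. Define that data cutoff.
3. Delete the measured-until-death and censoring text from ORR in Section 8.2.1 and the synopsis. Under OS, in Section 8.4 and the synopsis, state that subjects not known to have died are censored at the date last known alive on or before the cutoff.
4. If the limit is kept for survival, use one clock start in both places, drop the 3- and 5-year OS rates, and give the 2-year rate only with its number at risk.

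The cost is wording plus a few remote contacts per survivor, which Section 7.4 already allows. If everyone would otherwise be capped, six-monthly contacts from 18 to 60 months after treatment add about 0.5 (scenario 1) to 1.2 (scenario 2) contacts per enrolled subject.
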